Before smoking the assigned research cigarette, participants will complete a **cigarette purchase task (CPT)**, a behavioral economics-based measure of cigarette reinforcement, which assesses hypothetical demand for cigarettes across a range of prices, and a **cross-price elasticity purchase task**, which assesses hypothetical demand for experimental cigarettes at increasing prices of an individual's preferred brand of cigarettes. Participants will also complete assessment of nicotine withdrawal and craving prior to smoking using the **Minnesota Nicotine Withdrawal Scale (MNWS)**¹⁵ and the **Questionnaire on Smoking Urges**¹⁶. Heart rate and blood pressure will be taken before smoking (some measurements may not be taken if sessions are completed remotely). After smoking, participants will complete assessments of subjective response to smoking with the **modified Cigarette Evaluation Questionnaire (mCEQ)**, the **Duke Sensory Questionnaire (DSQ)**, and the **Nicotine Drug Effects Questionnaire (NDEQ)**. Participants will also complete the MNWS again.

The **Predicted Behavior Questionnaire** will be asked at the beginning of Visits 3 and 4, prior to when the VLNC is smoked. It asks participants to indicate their intentions to use cigarettes and other tobacco products when cigarettes have lower nicotine content and come menthol or non-menthol flavor. The **Expected Utility Questionnaire** will also be administered at Visits 3 and 4, before participants smoke. This questionnaire asks the degree to which participants would use the study cigarettes they just smoked for the past week (menthol or non-menthol) would help them quitting, be less dangerous than smoking, give up tobacco use, smoker fewer cigarettes, etc.

Participants will report their perceptions of the health risks associated with both their usual brand and their study cigarette brand using the **Perceived Health Risks Assessment**.¹⁷

ECOLOGICAL MOMENTARY ASSESSMENT (EMA)

C.5 EMA Procedure. Participants will record cigarette smoking and alternative tobacco use, craving, symptoms of withdrawal, and subjective ratings (e.g., satisfaction, reward, craving reduction, physical sensations like throat hit) associated with smoking the most recent cigarette in response to 2 random prompts to their phone each day. We will use a mobile EMA application, in which participants answer a set of survey questions on their cell phone by selecting

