responses on their mobile phone screen. [name] is currently using this EMA platform in her ongoing R01 with YAs, and it has been used it in many prior studies of smoking behavior.^{71,73,74} The selected monitoring schedule was driven by the study aims, and will allow us to capture a random sample of smoking episodes and to characterize variation in smoking reinforcement, craving, and withdrawal within-days and across days.^{147,148} Asking participants to record every smoking episode would be too burdensome and could result in substantial attrition. To ensure we capture smoking episodes for smokers who may be exclusively stimulus-based (e.g., morning only, evening only),¹⁴⁹ we will use an adaptive random prompting schedule that is programmed to coincide with the participant's sleep-wake cycle (e.g., time they wake up, time they go to bed), which will be collected at baseline.

Participants will be able to directly access the EMA survey upon receiving a prompt (vibration or “ping”) to their phone by touching the screen. EMA entries are expected to last ~5 minutes (based on response times in prior studies conducted by the PI),^{111,113} will be date- and time-stamped, and recorded immediately. To enhance compliance, we will provide detailed training on EMA and monetary incentives (see section 2.5. Recruitment and Retention Plan for more detail on monetary incentives). Pre-paid phones or reimbursement for cellular service will be provided (at the participant's choosing). Pre-paid phones will be labeled “government property”. At the 30-day follow-up, participants will complete a brief survey of satisfaction with and reactivity to EMA and another ETM where they will select VLNCs when menthol is banned in all combustible tobacco products, including cigarettes, hookah, little cigars, etc., but not banned in e-cigarettes.

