Participants will be involved in the study for approximately 2 months. There will be 5 in-person study visits (or virtual sessions) and a total of 21 days of daily monitoring of cigarette smoking behavior. There will be a 30-day follow-up after visit 5, that will be conducted either in person or over the telephone.

4. Describe blinding, including justification for blinding or not blinding the trial.

We considered blinding participants to the nicotine content in the research cigarettes to minimize the possibility that perceptions of these cigarettes may impact ratings of appeal/reinforcement and use behavior (e.g., compensatory behavior). We ultimately chose not blind participants so that we could model real-world conditions in which participants would be aware of the nicotine content of the cigarettes they smoke. [name], our consultant, is taking this same approach (e.g., not blinding participants) in a pilot study conducted as part of her U54. While we know about responses to VLNCs in a blinded scenario, findings from our study will be one of the first to inform VLNC work in an un-blinded scenario with young people.

5. Include justification for inclusion of a placebo or non-treatment group.

N/A. This is not a treatment study.

6. Describe what happens to participants receiving therapy when study ends or if their participation in the study ends prematurely.

N/A. This is not a treatment study.

7. Indicate where the procedures will be completed.

All participant recruitment, enrollment and testing will occur at the research laboratory of the TSET Health Promotion Research Center (HPRC) in Oklahoma City, OK. HPRC has conducted smoking research for the past 5 years.

8. Indicate whether clinically relevant research results, including individual research results, will be disclosed to participants. If so, under what conditions?

Females will be asked to take a pregnancy test at each in-person (or virtual) session prior to smoking, to determine eligibility. If a woman is pregnant, she will be given the results of her test immediately. If the session is completed remotely,

pregnancy tests will be provided to the participant before the session (mailed or curb-side pick-up) and pregnancy will be confirmed prior to beginning a smoking session.

9. Identifiers might be removed and the de-identified information may be used for future research without additional informed consent from the subject.

D. Biospecimens

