The participants may benefit directly through increased understanding of factors underlying uptake, appeal, and use of cigarettes or other tobacco products. This study is designed to answer important questions about factors that promote tobacco use behavior with the ultimate goal of informing prevention and

regulatory decisions about menthol cigarettes and other flavored tobacco products. Improved regulation could ultimately help deter tobacco use among the larger population of young people, thus decreasing overall rates of tobacco-related morbidity and mortality, including those that stem from tobacco use and dependence.

J. Statistical Methods

1. **Power:** All assessment methods of this proposal (laboratory, EMA, ETM) are adequately powered to test the primary outcomes of interest. Participants will be $n = 100$ menthol smokers aged 18-34 years. We will over-recruit for $n = 132$ to account for a conservative 20% attrition rate over the course of the study; with an estimated final analytic sample size of $n = 100$. We have specifically accounted for potential study drop-outs, un-enrollments due to changes in eligibility or AE/SAEs, and those who are lost to follow-up in our estimated 20% attrition rate. Attrition rate estimate based on previous studies conducted by Co-Investigators [name] and [name], and by consultant [name]. We based our sample size on effect sizes calculated from similar studies that tested the effect of VLNC cigarettes on adult participants across 6 to 20 weeks of exposure ^{18, 19}. A sample size of 100 participants would allow us sufficient power (defined as 0.8) to detect differences observed in adult cigarette smokers on the primary outcomes of interest. We will also recruit an additional $n = 40$ SGM menthol smokers aged 18-34 years with the supplemental funds recently obtained from the NIH. We anticipate that 15% of the parent grant sample will endorse being SGM ($n = 15$), based on PI [name]'s ongoing data collection efforts; thus, leaving a total sample of $n = 55$ SGM respondents (inclusive of the supplemental sample)

2. Laboratory Analyses (Aim 1)

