Patterns of missing data, compliance, distributional properties of variables, and correlations among all measures will be assessed. We will control for potential variables related to missing data and utilize multiple imputation methods (expectation maximization algorithm).¹⁶⁰⁻¹⁶³ Analysis will use linear mixed modeling with random subjects effects^{164,165} to assess the main effect of cigarette type on the primary and secondary outcomes of interest. Models will use a contrast to compare differences between menthol VLNC and non-menthol VLNC at the day-level on predictions of the outcome of interest and that outcome of interest at time t (e.g., morning) predicting behavior (number of cigarettes, any smoking, craving, withdrawal) occurring at a subsequent time point (controlling for cigarette consumption from the previous report). Comparison of usual brand and the menthol VLNC ratings will also be made to determine the perceived similarity of the VLNC to one's own brand. A sub-group of respondents may have fixed (unchanging) ratings of subjective response, craving, cigarettes per day, or withdrawal over the course of 7 days, although this is unlikely given the team's previous research. We will examine baseline and daily factors that set "no changers" apart from those whose show fluctuations in these factors, and examine these as potential covariates in models. Within-person slopes capturing associations between cigarette type and the EMA outcome of interest will be saved in regression models and used to predict the ETM responses.

4. ETM Analyses (Aim 3)

Primary Outcomes: (a) consumption of alternative tobacco products (milligrams of nicotine for alternative tobacco sources) as a function of cigarette type available. Typically, as cigarette price increases, consumption of other tobacco products increases.¹⁴ Secondary Outcomes: (a) breakpoint: the first price at which consumption of the available cigarette is zero; (b) intensity of demand: consumption at the lowest price); (c) elasticity of demand: sensitivity of cigarette consumption to increases in cost, (d) Omax: maximum expenditure for cigarette type available; and (e) Pmax: price at which expenditure is maximized.

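### The lagged EMA model in Aim 2 does not separate within-person from between-person variation in its time-t predictor, so a lagged coefficient may partly reflect stable differences between smokers

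*Combined protocol and SAP*

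**What the plan says.** Section J.3 (EMA Analyses, Aim 2) sets the model class: "Analysis will use linear mixed modeling with random subjects effects". Besides the cigarette-type comparison, it describes a lagged model with the "outcome of interest at time t (e.g., morning) predicting behavior (number of cigarettes, any smoking, craving, withdrawal) occurring at a subsequent time point". Previous-report consumption is the only covariate named for that model ("controlling for cigarette consumption from the previous report").

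The data come from answers "in response to 2 random prompts to their phone each day" (section C.5), over "a total of 21 days of daily monitoring of cigarette smoking behavior" (section on duration and number of visits). C.5 says the schedule was chosen partly "to characterize variation in smoking reinforcement, craving, and withdrawal within-days and across days". The background text on EMA (A.3) also values the method for preserving the order of events and allowing causal sequencing.

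Nothing in the supplied text mentions person-mean centring, person means as covariates, or any other within/between split of the lagged predictor. The within-person slopes mentioned later in J.3 are slopes on cigarette type, not on lagged ratings. The covariates meant to describe participants whose ratings never change do not separate the two levels either.

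**The concern.** The natural question for a lagged EMA model is momentary: when a person craves more than is usual for that person, does more smoking follow? A random subject intercept is assumed to be uncorrelated with the predictors. That is doubtful here. The trial enrols both someday and everyday smokers, and people who generally crave more may also generally smoke more. An unsplit rating then carries two signals, who the person is and how the person feels now, and the model returns one weighted blend of them.

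A significant coefficient could be reported as momentary reinforcement driving later smoking when it shows only that heavier smokers rate higher. This is the analysis that uses the time ordering of the EMA data, in a study intended to inform regulation.

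**Working it through.** The plan states no alpha, ICC, correlation or effect size for the lagged model, so it has no figure of its own to reproduce.

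**Inputs from the documents**
- Participants: 100 (section J.1, "A sample size of 100 participants would allow us sufficient power (defined as 0.8"), or 138 with the supplement sample (C.4; 172 × 0.8 = 137.6).
- Prompts: 21 × 2 = 42, matching the compensation table.
- Same-day pairs per person: 7 in one condition, 14 over both VLNC weeks, 21 in all.
- Consecutive-prompt pairs: 14 − 1 = 13 per week, so 26 over both VLNC weeks and 39 in all.

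**Assumptions**
- Two-sided 5% test.
- ICC 0.5 for predictor and outcome.
- Between-person correlation ρ from 0 to 0.5.
- True within-person lagged effect zero.
- Complete data, normal outcomes, no serial correlation.

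**Hand calculation.** Let person-level and momentary variances both be 0.5, with m pairs per person and n people. The random-intercept fit down-weights between-person information by 0.5/(0.5 + 0.5m) = 1/(m + 1).
- Within-person sum of squares per person: 0.5(m − 1).
- Weighted between-person part: 0.5(m + 1)/(m + 1) = 0.5.
- Between-person share of the coefficient: 0.5/[0.5(m − 1) + 0.5] = 1/m.
- Between-person slope: 0.5ρ/(0.5 + 0.5/m) = ρm/(m + 1).
- Bias = (1/m) × ρm/(m + 1) = ρ/(m + 1).
- SE = √[0.5/(n × 0.5m)] = 1/√(nm).

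For n = 100, m = 14, ρ = 0.5: bias = 0.5/15 = 0.033, SE = 1/√1400 = 0.0267, expected z = 1.25. Rejection = Φ(1.25 − 1.96) + Φ(−1.25 − 1.96) ≈ 24%. This leaves out the consumption covariate and treats the variances as known.

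**Simulation.** A random-intercept REML fit with the unsplit predictor, cigarette type and previous-report cigarettes; 3000 runs per cell (Monte Carlo SE about 0.4 points at 5%, 0.9 at 40%). Percent rejecting:

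| n, pairs | ρ = 0 | 0.1 | 0.2 | 0.3 | 0.5 | hand formula at 0.5 |
|---|---|---|---|---|---|---|
| 100, 7 | 4.7 | 6.3 | 9.6 | 16.9 | 39.6 | 38.0 |
| 100, 14 | 5.2 | 5.6 | 7.5 | 13.9 | 24.1 | 23.9 |
| 100, 21 | 5.4 | 6.5 | 7.4 | 10.5 | 18.5 | 18.1 |
| 100, 26 | 4.0 | 5.4 | 6.9 | 8.6 | 14.8 | 15.7 |
| 100, 39 | 4.3 | 4.9 | 6.2 | 7.4 | 12.8 | 12.2 |
| 138, 14 | 5.3 | 6.2 | 9.6 | 14.1 | 31.7 | 31.1 |

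The simulated bias at ρ = 0.3 to 0.5 is 0.008 to 0.064 SD per SD.

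**Variations**
- ICC matters less: at n = 100, 14 pairs, ρ = 0.5, rejection is 22% at ICC 0.3 and 28% at ICC 0.7.
- The consumption covariate does not remove the inflation. With cigarettes as the outcome, rejection is about 31% (n = 100, 14 pairs, ICC 0.5, ρ = 0.5).
- A random slope on the unsplit predictor still gives 19% (300 runs).
- The cigarette-type effect and the type-by-rating interaction reject 3.4-6.4% in every setting tried.
- With the predictor split into mean and deviation, the deviation coefficient rejects 4.2-6.1% over all the 3000-run settings.

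**The case against.** The strongest reply is that the plan is silent rather than wrong. A reader might infer that J.3 prescribes raw ratings with a random intercept only. It does not: it says random subject effects and leaves both centring and random slopes open. This stands, and the defect is one of specification. It still matters, because fitting the model literally gives the blended coefficient, and a choice left until the data are seen adds discretion.

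Nor do the documents say outright that the lagged coefficient will be read as within-person. As a blended predictive association it is not a false positive. That is also fair, but the emphasis on sequencing and on within-day variation makes the momentary reading the likely one.

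A reader might further infer that error rates exceed 5% regardless, or that the main Aim 2 comparison is compromised. Neither is supported. Inflation is negligible at a correlation of 0.1 or below, and the menthol versus non-menthol contrast is a within-subject comparison that stays near nominal. The Aim 2 hypotheses contain no lagged effect.

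It is also tempting to argue that random prompts often fail to yield a morning-to-evening pair and that the app should change. C.5 describes adaptive prompting tied to each person's sleep-wake cycle, morning is only an example in J.3, and any two answered prompts are ordered in time. No timing figures are given from which a shortfall could be computed.

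Finally, the split is not a complete cure. If earlier smoking affects the next rating, the deviation coefficient is itself biased. In checks at n = 100 with 14 pairs, it rejected about 8-9% at an assumed feedback correlation of 0.2 and 17-20% at 0.4, sometimes worse than the unsplit predictor. With 7 pairs the range was 11.5-27.9% over feedback of 0.2 to 0.4. This stands as a limitation to be stated.

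**Conclusion.** The point holds as a gap in specification confined to the lagged main effect. Unless person means are separated, a within-person reading carries a false-positive rate of about 5% if the between-person correlation is 0 to 0.1, about 7-17% at 0.3 and about 13-40% at 0.5. It falls with more pairs per person and rises with more participants. These rates rest on the assumed correlations and ICC, a two-sided 5% test, and complete normal data; the binary any-smoking outcome was not simulated. The bias is small in absolute terms, so the risk is a nominally significant but spurious finding rather than a large distorted effect. The documents do not support extending the criticism to the cigarette-type contrast, its interaction with the lagged rating, or the prompting schedule. The gap should be closed before the lagged models are run.

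**What to change.** In J.3, state that each time-t predictor enters the lagged model as two terms, the person's mean over the pairs analysed and the deviation from that mean, and that only the deviation coefficient is interpreted as the within-person effect. The unsplit model is the special case in which the two coefficients are equal, so nothing is lost by fitting both. Keep the planned adjustment for previous-report cigarettes and add a sensitivity analysis without it.

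The cost is a sentence or two of SAP text and one derived variable per predictor, with no new data and no participant burden. Under the assumptions above, intervals widen by √[m/(m − 1)]: about 8% at 7 pairs, 4% at 14 and 1% at 39. The plan should also acknowledge that some bias remains in the deviation coefficient if earlier smoking affects later ratings. No change to the EMA app is needed.

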C.5.b. EMA Measures. EMA measurements will parallel the constructs used in the laboratory assessments (e.g., craving, subjective response) and have established psychometric properties.^{66,68,111,150-154} Subjective ratings will be queried using items from the mCEQ, which has been pilot tested for EMA deployment by the PI and is being deployed via EMA for her ongoing R01. Questions will also assess the use of alternative tobacco products since the previous assessment, characterizing flavors (e.g., fruit, chocolate), use of usual brand cigarettes, craving, withdrawal, and factors associated with smoking (life events, mood, peer use, alcohol, other drug use) that have been used in prior EMA studies by the PI and others. To minimize response burden, EMA will prompt use-relevant probes via skip patterns. Missed EMA assessments will be retrospectively assessed by phone or online via a REDCap survey.

Following are the standard procedures that have been adopted for OUM/OUHSC for all studies that will be facilitated in-person and would be utilized for this study in response to COVID-19.

PROCEDURE:

1. Employees will comply with all OUHSC COVID related policies and procedures as currently exist and as are revised in the future.
2. Efforts will be made to minimize face-to-face time with participants. When possible, consents will be sent to participants at their homes and reviewed by phone or zoom, as available. Additional items, including pregnancy tests, will also be shipped to the home, and reviewed over phone or zoom, when possible.
3. During scheduling, participants will be asked to wear a mask, if they have one available, to their appointments. For participants who do not have access to a face mask, one will be provided. They will also be asked the questions from the OUM/OUHSC COVID19 Questionnaire (see attached in “Other Documents”).
4. If the patient is symptomatic or has known direct contact with a person with COVID-19 they will not be able to attend a study session and will be asked to consult with their PCP prior to re-scheduling the visit.

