Visit 5 (Experimental Tobacco Marketplace)	\$ 50
Bonus for eligible referral	\$20
Bonus for scheduling and attending first visit within 5 days of phone screening	\$20
EMA	

Call completion (*42 calls)	\$1/call (\$42 total)
Bonus for completing all calls each week (* 3 weeks)	\$10/week (\$30 total)
Bonus for completing 85% of calls for 3 weeks	\$45
Total possible EMA	\$117
Research Cigarette Compliance	
Returned used cigarettes	\$7 maximum/week @ 2 weeks
Returned unused cigarettes (\$0.25/cigarette)	\$20 maximum/participant
Returned empty packs (\$1/pack)	\$5 maximum/participant
Total possible cigarette compliance	\$14 + \$20 + \$5 = \$39
30-Day Follow-up	
30-day Follow-Up + ETM 3	\$45
Travel for In Person or Curbside Pick-up/Drop-Off	
\$10 for each in person visit/curbside pick-up/drop-off of study materials @ 4 visits	\$40 maximum/participant
Bonus for completing all phases	\$ 70
Maximum Total	\$ 571

To enhance retention in all phases of the study, due to higher than anticipated loss-to-follow-up, we will offer a bonus of missed incentive amounts to participants who are hard-to-reach or schedule. With this bonus, participants will be eligible to receive missed compensation opportunities, if they complete remaining in-person study sessions and/or surveys. Missed opportunities may include the bonus for scheduling and attending the first visit within 5 days of phone screening (\$20), the eligible referral bonus (\$20), bonuses for completing all EMA surveys each week (\$30 maximum) even if they miss some surveys, bonus for completing 85% of EMA surveys for 3 weeks (\$45) even if they miss some surveys, and the bonus for completing all phases of the study (\$70). Enhancement bonuses will be separated into \$20 increments to encourage a participant to attend any remaining session(s) they have not completed. After the final in person session is complete, the participant will be eligible for all remaining compensation amount not already claimed, up to the maximum of \$571, even if they may not have met the full criteria. Thus, we calculate their maximum bonus amount allotted to participant, and give it to them in \$20 increments (per number of sessions attended). When they complete the final in-person visit, they are eligible for all remaining bonus/compensation to get the maximum amount (\$571).

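### The lagged EMA models of later tobacco use omit the hours each report covers; if use is counted from prompt to prompt and ratings drift over the day, random prompt timing can produce a false association with later smoking.

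*Combined protocol and SAP*

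**What the plan says.** J.3 (EMA Analyses, Aim 2) specifies linear mixed models with random subject effects. Besides the contrast between the two VLNC types, it plans models in which a report at one time, for instance the morning, is used for "predicting behavior (number of cigarettes, any smoking, craving, withdrawal) occurring at a subsequent time point (controlling for cigarette consumption from the previous report"). Consumption at the previous report is the only adjustment named. No elapsed time, offset or time of day is mentioned.

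C.5 (EMA Procedure) has participants report "in response to 2 random prompts to their phone each day", on an "adaptive random prompting schedule that is programmed to coincide with the" participant's sleep-wake cycle, which is recorded at baseline. No prompt blocks, window widths or minimum gap are given. Entries "will be date- and time-stamped, and recorded immediately".

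C.5.b (EMA Measures) asks about "use of alternative tobacco products since the previous assessment". No recall window is given for cigarettes, and J.3 describes the research-cigarette outcome as both within-day and per day.

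The plan has "a total of 21 days of daily monitoring of cigarette smoking behavior". Two prompts x 7 days x 3 periods = 42, which agrees with the compensation table.

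**The concern.** A count of cigarettes since the last prompt depends on how often the person smokes and on how long the interval was. When prompts fall at random, chance sets the interval. It is also tied to the clock: the later a prompt falls, the less time tends to remain before the next one. Suppose craving, satisfaction or withdrawal changes steadily over the day. A late prompt then carries a systematically different rating and is followed by a shorter window with fewer cigarettes, so rating and later count are correlated within person with no behavioural link.

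The previous count does not remove this. It is a noisy stand-in for the previous window and so only a partial proxy for the clock time of the prompt.

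The sign follows the drift. Ratings that rise through the day give a false negative slope. Ratings that fall give a false positive one, which would read as appeal or craving driving later smoking, the very question these models address. Even with no drift, unmodelled variation in window length is noise in the outcome and costs precision.

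**Working it through.** The documents give no hours per count and no error rate for the lagged model, so there is no plan figure to reproduce. From the documents: two random prompts a day, 7-day periods (14 VLNC days in all), a linear mixed model with the previous count as covariate, and n = 100 (J.1). Assumed: waking day W = 16 h, one uniform prompt in each half-day, 10 cigarettes per day at a constant Poisson rate (λ = 10/16 = 0.625 per hour), and ratings equal to drift b x clock time plus unit-variance noise.

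**Window length.** The gap between consecutive prompts is triangular on 0 to W.
- Mean 8 h; variance 2 x 8²/12 = 10.67; SD 3.27 h.
- 5th percentile W√(0.05/2) = 16 x 0.158 = 2.5 h; 95th percentile 16 − 2.5 = 13.5 h.
- Correlation of the gap with the clock time that starts it: −1/√2 = −0.71.

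Other assumptions change the 5th to 95th percentile range: 2.2 to 11.8 h for a 14 h day; 2.9 to 15.2 h for an 18 h day; 0.4 to 12.4 h within day for two unrestricted prompts in 16 h; 6.6 to 9.4 h for 2-hour prompt windows.

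**Share of count variance due to window length**, λ²Var(w) / [λ²Var(w) + λE(w)]:
- 10 per day: 4.17 / (4.17 + 5.00) = 45%.
- 3 per day (λ = 0.1875): 0.375 / (0.375 + 1.5) = 20%.

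Removing 45% of the variance should shrink the standard error by 1 − √0.55 = 26%. Simulation at zero drift gave 0.089 falling to 0.067, about 25%.

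**Expected false slope, same-day lag, no previous count:** −λb Var(T) / (1 + b²Var(T)), with Var(T) = 8²/12 = 5.33. For a drift of 1 SD across the day, b = 1/16 = 0.0625, giving −0.208/1.021 = −0.204 cigarettes per rating unit. Simulation gave −0.198. Adding the planned previous count reduced it only to −0.152.

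**False-positive rate at nominal 5%, no true link, planned previous-count term included, all consecutive lags, half-day prompts:**

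| Drift, SD per hour (SD over 16 h) | 0.02 (0.32) | 0.05 (0.80) | 0.10 (1.60) |
|---|---|---|---|
| 7 days, 10 per day | 9% | 30% | 72% |
| 14 days, 10 per day | 15% | 57% | 98% |

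Hours added: about 4 to 7%. Repeat runs of the one-week setting gave 8%, 26 to 36% and 72 to 82%. In the run that gave 8%, 36% and 82%, lowering consumption to 3 per day gave 8%, 24% and 58%.

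**Dependence on the prompt schedule** (14 days, 10 per day, within-person linear model, previous count included, 400 runs per cell):

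| Drift across the day, SD | 0 | 0.25 | 0.5 | 1.0 |
|---|---|---|---|---|
| Half-day, same-day lag | 5.2% | 8.5% | 17.7% | 41.5% |
| Half-day, all lags | 7.7% | 8.5% | 19.3% | 72.5% |
| Unrestricted, same-day lag | 4.0% | 9.8% | 20.3% | 56.5% |
| Unrestricted, all lags | 5.2% | 4.8% | 9.2% | 22.3% |
| 2-hour windows, same-day lag | 5.0% | 5.5% | 3.7% | 6.2% |

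With hours in the model every scenario fell between 3.0% and 6.8%.

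**The planned form**, a linear mixed model with random intercept (half-day, same-day lag, 120 runs): 2.5%, 17.5% and 48.3% at drifts of 0, 0.5 and 1.0 SD across the day. Adding hours brought the last two to 2.5% and 5.0%.

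**The case against.** The strongest reply is that much of this is not in the documents, and that is largely right.

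- **Recall window.** The since-last-assessment period is written for alternative products only, and one phrase in J.3 could describe a daily cigarette count. However, the lagged model needs a quantity that differs between one report and the next, and it refers to consumption from the previous report. Between-prompt counting is therefore the more natural reading, but it remains an inference.
- **Prompt windows.** A reader might infer that each count covers 2.5 to 13.5 hours. That is a 5th to 95th percentile range under an assumed day and schedule. The stated schedule also permits narrow windows, and with 2-hour windows the problem all but disappears.
- **Drift and smoking rate.** C.5 expects ratings to vary within days but gives no direction or size. The 98% figure needs a drift of 1.6 SD over the waking day, which nothing in the documents supports. Someday smokers are eligible, so 10 per day may be too high, and a constant rate is a simplification. A reader might conclude that a false effect is likely; the documents show only that it is possible.
- **Reach.** A reader might also infer that the Aim 2 comparison is compromised. It is not: prompt timing does not depend on cigarette type, so the menthol versus non-menthol VLNC contrast is not biased by this mechanism. Craving and withdrawal are not counts over an interval.

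What stands is that J.3 omits exposure time from lagged models of use under random prompting, and that the previous count does not substitute for it.

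**Conclusion.** The point holds conditionally, for the lagged models of use: number of cigarettes, any smoking by the same logic, and alternative-product use if it is modelled this way. Bias requires counts that run from prompt to prompt, reasonably wide prompt windows, and ratings that drift with clock time. When all three hold, the false-positive rate runs from modest to severe: about 9% to 72% over one week and 15% to 98% over two, across the drifts examined at 10 cigarettes per day. It is lower at 3 per day, or with unrestricted prompts over all consecutive lags, and near nominal without drift. The precision gain of about 25% needs no drift but is specific to the half-day schedule at 10 per day.

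This is a specification gap worth closing in a supporting analysis. It is not a threat to the main comparison of cigarette types.

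**What to change.** In J.3:

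1. Derive waking hours since the previous answered report from the time stamps and the baseline sleep-wake times.
2. Enter hours in the lagged use models, as a covariate in the linear mixed model or as a log(hours) offset in a count model, together with the clock time of the prompt.
3. State the recall window of the cigarette item. C.5.b has missed assessments completed retrospectively, so say also which interval such an answer covers.

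In the non-lagged use models the hours term is optional and serves precision only.

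The cost is one derived variable and one or two model terms. The inputs are already collected, and no procedure or participant burden changes.
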